Endpoint	Primary Endpoint: Opioid utilization for the first 72 hours after surgery, including during surgery, calculated as morphine equivalent. Secondary Endpoints: Opioid consumption Post-operatively Patient reported VAS scores in PACU Length of stay in PACU Patient reported VAS scores on POD 1, POD 2, POD 3, POD 7 Reaction to IPACK block Incidence of postoperative complications
Study Duration	The study will continue until 50 subjects are enrolled per arm, to allow for potential dropout and increased power.
Participant Duration	Each participant will be enrolled on DOS and complete their final follow up on postoperative day seven.
Duration of IP administration	Once during surgery
Population	50 patients per study arm scheduled for ACLR with BPTB autograft
Study Sites	NYU Langone Orthopedic Hospital and NYU Ambulatory Surgery Center at 38 th street
Number of participants	100
Description of Study Agent/Procedure	Patients in both the study and control group will receive the standard of care adductor canal block composed of 15 mL of Bupivacaine (0.25%). Patients in the study group will receive the additional IPACK block performed using 20 mL of Bupivacaine (0.25%) injected into the interspace between the popliteal artery and capsule of the knee. Patients will be blinded to their group allocation.
Reference Therapy	Reference is isolated adductor canal block
Key Procedures	Adductor canal block 15 mL 0.25% Bupivacaine, IPACK block with 20 mL 0.25% bupivacaine

CONFIDENTIAL

This material is the property of the NYU School of Medicine and Langone Medical Center. Do not disclose or use except as authorized in writing by the study sponsor

Statistical Analysis	Continuous and categorical baseline characteristics will be compared using Hedges standardized difference. Normally distributed data will be compared using t tests while non-normally distributed continuous outcomes will be assessed using the Mann-Whitney U test.
----------------------	--

CONFIDENTIAL

This material is the property of the NYU School of Medicine and Langone Medical Center. Do not disclose or use except as authorized in writing by the study sponsor

1 Background and Specific Aims

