TREATMENT PHASE:

Patients in both the study and control group will receive the standard of care adductor canal block. This consists of 15mL of bupivacaine (0.25%) Injected under ultrasound guidance in the saphenous nerve via the adductor canal. Patients in the study group will receive the additional IPACK block performed using 20 mL of bupivacaine (0.25%) injected into the interspace between the popliteal artery and capsule of the knee.

[figure not shown]
POST-OPERATIVE PHASE:

After initial recruitment, subjects' pain will be assessed via visual analog scale (VAS) by nursing staff during the post-operative period as per standard of care in the post anesthesia care unit, and by the research staff prior to leaving the surgical center. The VAS pain scores are collected and documented in the patient's electronic medical record. Additionally, a standardized regimen of pain medication will be given to all subjects who are enrolled. The pain medications given to patients are standard of care medication 325-5 mg Percocet and vary based on pain level. This is determined by the clinical staff caring for each patient. While the patient is in the PACU prior to discharge, an authorized research member will visit the patient and obtain a pain score using the VAS and McGill Pain Scale. Data on PACU opioid use documented in the electronic medical record will be collected. On POD1, POD 2 and POD 3, a phone call or email survey will be sent to the patient to collect additional data on opioid use at home as well as a VAS score at 24, 48, and 72 hours after surgery.

CONFIDENTIAL

This material is the property of the NYU School of Medicine and Langone Medical Center. Do not disclose or use except as authorized in writing by the study sponsor

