5.1 Potential risks

Medication and Procedure

CONFIDENTIAL

This material is the property of the NYU School of Medicine and Langone Medical Center. Do not disclose or use except as authorized in writing by the study sponsor

The potential risks associated with bupivacaine include neurologic and cardiac toxicity, if injected intravascularly. However, the risk is very low because a trained anesthesiologist using ultrasound guidance will perform both the IPACK block and ACB. US guidance allows the anesthesiologist to see and avoid blood vessels when administering the medication. Additionally, the syringe of the local anesthetic will be aspirated prior to injection by the anesthesiologist and surgeon to ensure that the block needle tip is not intravascular.

The risk of nerve injury or intravascular injection in the IPACK block is similar to the standard ACB arm of the study. Risk of infection at the injection site due to the expertise of the anesthesiologist performing the block under ultrasound guidance under sterile conditions to avoid infection risk. Allergic reactions to local anesthetic is possible however, any subjects with a history of allergies to local anesthetic will be excluded from the study.

At the time of the nerve block, the anesthesiologist who is providing the injection under ultrasound will monitor the subject's vitals, respiratory and cardiac status to assess for the aforementioned risk of neurologic or cardiac toxicity, as suggested in the Bupivacaine package insert. Subsequently, patients will be monitored in the post anesthesia care unit per standard of care for any adverse effects of the nerve block including nausea, vomiting, blurred vision, and infection at the injection site. Both the ACB and ACB plus IPACK block are used as standard of care at this institution depending on treatment physician's preference.

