5.2 Potential benefits

Study subjects may experience better pain control, improved satisfaction, decreased need for opioids and reduced incidence of side effects. If the study is not inconclusive, the study's results may benefit future patients by showcasing that addition of IPACK block improves pain control in the first 24 hours of an ACLR.

6 Statistical Analysis

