6.2 Analysis of Endpoints

Primary Endpoints:

1. Opioid utilization for the first 24 hours after surgery, including during surgery, calculated as oral morphine equivalent.

CONFIDENTIAL

This material is the property of the NYU School of Medicine and Langone Medical Center. Do not disclose or use except as authorized in writing by the study sponsor

Secondary Endpoints:

1. Patient reported VAS scores in PACU
2. Length of stay in PACU
3. Patient reported VAS scores on POD 1, POD 2, POD 3, POD7
4. Reaction to IPACK block
5. Mid-term functional outcomes will be assessed at 6 months: VAS, KOOS-PS, KUJALA, Tegner Activity Scale, strength, ROM.

Normally distributed data such as the primary outcome variable will be compared using the two-sample t-test. In the case that the data are not normally distributed, the Wilcoxon rank-sum test will be used instead. Categorical variable will be compared using the Chi-Squares unless other tests such as the Fisher's exact test are more appropriate.

All endpoints will be evaluated as fits the data set with graphical figures such as scatter plots, box-and-whisker plots, and frequency histograms to visualize the distribution of these outcomes and their relationships to covariates and treatment assignment. When appropriate descriptive graphical and tabular methods will also be estimated and presented in a graphical figure.

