7.6 Safety Oversight

It is the responsibility of the Principal Investigator [name], and co-investigators [name] MD and [name] MD to oversee the safety of the study at his/her site. This safety monitoring will include careful assessment and appropriate reporting of adverse events as noted above, as well as the construction and implementation of a site data and safety-monitoring plan. Adverse Events such as development of an allergy to local anesthetic, inadvertent intravascular injection of local anesthetic and infection at site of injection will be reviewed every three months. Serious adverse events are rare and are unlikely to occur but if a serious adverse event occurs, steps will be taken to address it. Study recruitment will cease temporarily while a data safety monitoring team convenes to review the event. Medical monitoring will include a regular assessment of the number and type of serious adverse events.

Data Safety Monitoring Plan

The principal investigator [name], and co-investigators [name] MD and [name] MD are responsible for data safety and monitoring of the overall study.

The following data points and outcomes will be reviewed during data safety monitoring reviews: number of patients enrolled, pain scores of patients, AEs and SAEs such as neuro and cardiotoxicity. Data will be monitored quarterly and will be reported at the time of continuing review.

The stopping rules for the study are adverse harm to patients, as measured by the serious adverse events, specifically neurotoxicity, cardiotoxicity, or allergic reaction to bupivacaine. A chi-square test will be used to determine if there is a statistically significant difference ($p<0.01$) in the rate of SAEs between treatment arms. If there is a statistically significant difference in the rates of SAEs between arms, accrual to the trial will be suspended while the study team and data safety monitoring team conduct an evaluation of the events.

The PI will oversee all study activities including data collection and management and will ensure study personnel conduct this study based on the approved protocol.

8 Source Documents and Access to Source Data/Documents

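### Section 6.2 lists no harm endpoint that can be compared between arms; the only prespecified between-arm safety test is the SAE monitoring rule in section 7.6

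*Combined protocol and SAP*

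**What the plan says.** Section 6.2 (Analysis of Endpoints) gives five secondary endpoints. The fourth, "Reaction to IPACK block", is the only one about harm. The Protocol Summary lists it too. Neither place gives a definition, event list, time window or grading. Section 6.2 then sets a general rule: chi-square for categorical variables, or another test such as Fisher's exact where that suits better.

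Sections 2, 2.1 and 4.1.1 give the IPACK injection to the experimental arm only. The Summary says of the comparator: "Reference is isolated adductor canal block". No sham injection is described.

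The Summary has a further secondary endpoint, "Incidence of postoperative complications", which does not appear in the section 6.2 list.

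Other safety text:
- Section 5.1 has PACU staff monitor patients "for any adverse effects of the nerve block including nausea, vomiting, blurred vision, and infection at the injection site".
- Section 5.2 names "decreased need for opioids and reduced incidence of side effects" among the possible benefits.
- Section 7.4 has all AEs documented in all participants, whatever their cause.
- Section 7.6 contains a monitoring rule: "A chi-square test will be used to determine if there is a statistically significant difference" (p<0.01) "in the rate of SAEs between treatment arms". A significant result suspends accrual while the events are evaluated.

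**The concern.** An endpoint named after a procedure that one arm does not receive cannot support a test between arms. A possible event would be set against an impossible one.

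The events that such an endpoint might pick up are not specific to IPACK. Nausea, vomiting, blurred vision and injection-site infection are listed in section 5.1 as effects of the nerve block, and both arms receive a block. Nausea and vomiting can also follow opioids. Under the current wording these events could enter the endpoint only in the IPACK arm, and only when someone attributes them to IPACK.

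That attribution may not be blinded. Only patients are described as blinded (section 2.1), the anesthesiologist receives the allocation envelope (section 6.4), the examining clinician judges causality (section 7.3.2), and no text requires that clinician to be unaware of allocation.

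At stake is whether the trial can say anything reliable about non-serious harms, including whether lower opioid use brings fewer side effects.

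**Working it through.** The plan gives no figure for this point, so there is none to reproduce. The check has three steps.

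**1. Can each harm item be compared between arms?**

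| Item | Where listed | Can occur in both arms? | Planned between-arm test |
|---|---|---|---|
| Reaction to the IPACK block | Summary and 6.2 | No, read literally | Chi-square or Fisher, by default under 6.2 |
| Postoperative complications | Summary only | Yes | Not in the 6.2 list |
| SAEs | 7.6 | Yes | Chi-square, p<0.01, as a monitoring rule |
| Non-serious AEs | Collected under 7.4 | Yes | None stated |

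No harm item in section 6.2 passes. The one valid between-arm test is in section 7.6 and covers SAEs only.

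**2. How far does the SAE rule fill the gap?** Inputs are 50 per arm (section 2) and p<0.01 (section 7.6). With e events in the experimental arm and 0 in control, the uncorrected statistic is

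X² = 100 × (50e)² / [e × (100 − e) × 50 × 50] = 100e / (100 − e).

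- 6 v 0: 600/94 = 6.38, p = 0.0115. The rule does not trigger.
- 7 v 0: 700/93 = 7.53, p = 0.0061. The rule triggers.
- 8 v 0: first trigger with Yates correction (p = 0.0099) or Fisher's exact test (p = 0.0058).
- 9 v 1: first trigger by uncorrected chi-square when there is one control SAE (p = 0.0077).

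At 7 v 0 the expected SAE count per arm is 7/2 = 3.5, below the usual 5 for a chi-square test.

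The protocol gives no SAE rate. Under assumed true rates (experimental v control), the chance that uncorrected chi-square reaches p<0.01 at full enrolment, by binomial enumeration, is:

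- 5% v 1%: 0.7%
- 10% v 2%: 10.7%
- 20% v 2%: 67%

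**3. What could attribution do to the IPACK item?** This is an illustration with assumed figures. Suppose 20% of each arm has nausea or vomiting, so 0.20 × 50 = 10 patients per arm and no true difference.

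- No IPACK-arm case attributed to the block: 0/50 v 0/50.
- Half attributed: 5/50 v 0/50, Fisher p = 0.056.
- All attributed: 10/50 v 0/50, Fisher p = 0.0012.

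The last line is an assumed worst case and not an estimate. The causality grading in section 7.3.2 weighs other explanations, so full attribution is unlikely. The sequence shows only that the result depends on labelling.

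**The case against.** **A reader might infer that the plan has no between-arm safety comparison at all, or that any harm comparison can only go against IPACK.** The documents support neither. The section 7.6 test compares SAE rates between arms and can go either way, and section 7.4 collects all AEs in both arms. The weaknesses in step 2 are limits of a comparison that exists.

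**The invalid test is inferred.** No sentence says that this particular endpoint will be tested between arms, and it could be read as a tolerability item described in one arm. That is fair, but section 6.2 does not say so. Its wording about fitting the data set concerns graphical displays, and its descriptive methods are additional to the tests. Nothing exempts the item from the general rule.

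**The content of the endpoint is unknown.** Nothing links the section 5.1 symptom list to it. Section 7.6 suggests another reading: allergy to local anesthetic, intravascular injection and site infection. This stands, and it is why the 20% illustration carries little weight. It also confirms that a definition is needed.

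**The omitted endpoint may be only a list mismatch.** The mismatch is wider than safety. Postoperative opioid consumption is in the Summary's secondary list but not in that of section 6.2, and the 6-month functional outcomes are in section 6.2 but not in the Summary. The conflict still leaves the section that governs analysis without a two-arm harm endpoint.

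**Fewer side effects is a possible benefit, not an aim.** That is correct. The point does not depend on treating it as an objective.

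**Conclusion.** The point holds in this limited form. Section 6.2 contains no harm endpoint that can be compared between arms. Its one harm item is undefined and, read literally, fixed at 0/50 in controls, and the Summary's two-arm item is missing. The SAE rule in section 7.6 is a real between-arm test, but it cannot stand in for a side-effect comparison. It covers serious events only, its stated consequence is suspension of accrual, and at full enrolment it needs 7 v 0 or 8 v 0 to trigger.

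The conclusion rests on a literal reading of the endpoint's name and on section 6.2 governing the analysis. The size of any bias cannot be estimated, because the protocol gives no event rates and no definition. The primary endpoint is not affected. This is a change that should be made, not a fault that undermines the trial.

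**What to change.** - **Replace the fourth secondary endpoint** in section 6.2 and in the Summary with adverse events from a fixed list, counted in both arms over the same stated window, whatever the attributed cause.
- **Report two components separately**, so that fewer opioid symptoms cannot hide more block events: block or local-anesthetic events (injection-site infection, local anesthetic toxicity, allergic reaction), and general or opioid-type symptoms (nausea, vomiting, blurred vision).
- **Name the analysis**: Fisher's exact test, or a risk difference with an exact confidence interval, since counts will be small.
- **Restore postoperative complications** to section 6.2, with a definition and a time window that do not overlap with the list above.
- **Report IPACK-attributed reactions descriptively** in the IPACK arm only, and state that no between-arm test applies.

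The cost is small but is more than rewording. AE capture in both arms (section 7.4) and PACU monitoring (section 5.1) already exist. The POD 1 to 3 contacts are described as collecting opioid use and VAS scores, so a short AE question set, asked the same way in both arms, would have to be added there and at the POD 7 visit. The analysis gains a few extra tables. No treatment or visit schedule changes.

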6.2.1 Baseline Descriptive Statistics

The following patient data will be recorded: age, gender, height, weight, MRI diagnosis date of admission, date of discharge, laterality, surgical approach, implants used, duration of surgery, concomitant procedure, contamination, ASA, comorbidities (smoking, cardiac history, diabetes etc.), and medications. This information will be accessible in the patient's medical record.

6.3 Sample Size

Using a 2-sided, 2-sample t test, an α value of 0.05, a power analysis revealed that 42 subjects were needed per group to detect a moderate effect size with a power of 0.80. We chose to enroll 50 subjects per arm to allow for potential dropout and an increased power.

6.4 Enrollment/Randomization/Masking Procedures

We will utilize randomization.com to generate a block randomization assignments for all 100 participants. Someone that is not a stakeholder in the study will make randomization envelopes, which include the study ID number, the treatment assignment, and dosage specifics. These randomization envelopes will then be distributed to the anesthesiologist pre-operatively by the authorized researcher after informed consent is obtained.

6.5 Breaking the Study Blind/Participant Code

If there is any adverse event related to the drug, we will break the blind for the subject and randomization will be disclosed to the patient.

7 Assessment of Safety

An **adverse event** (AE) is any symptom, sign, illness or experience that develops or worsens in severity during the course of the study. Intercurrent illnesses or injuries should be regarded as adverse events. Abnormal results of diagnostic procedures are considered to be adverse events if the abnormality:

- results in study withdrawal
- is associated with a serious adverse event
- is associated with clinical signs or symptoms
- leads to additional treatment or to further diagnostic tests
- is considered by the investigator to be of clinical significance

CONFIDENTIAL

This material is the property of the NYU School of Medicine and Langone Medical Center. Do not disclose or use except as authorized in writing by the study sponsor

7.1 **Definition of Adverse Events (AE)**

Serious Adverse Event

Adverse events are classified as serious or non-serious. A **serious adverse event** is any AE that is:

- fatal
- life-threatening
- requires or prolongs hospital stay
- results in persistent or significant disability or incapacity
- a congenital anomaly or birth defect
- an important medical event

Important medical events are those that may not be immediately life threatening but are clearly of major clinical significance. They may jeopardize the subject and may require intervention to prevent one of the other serious outcomes noted above. For example, drug overdose or abuse, a seizure that did not result in in-patient hospitalization, or intensive treatment of bronchospasm in an emergency department would typically be considered serious.

All adverse events that do not meet any of the criteria for serious should be regarded as **non-serious adverse events**.

7.2 **Definition of Unanticipated Problems (UP)**

Unanticipated Problems Involving Risk to Subjects or Others

Any incident, experience, or outcome that meets all of the following criteria:

- Unexpected in nature, severity, or frequency (i.e., not described in study-related documents such as the IRB-approved protocol or consent form, the investigators brochure, etc)
- Related or possibly related to participation in the research (i.e., possibly related means there is a reasonable possibility that the incident experience, or outcome may have been caused by the procedures involved in the research)
- Suggests that the research places subjects or others at greater risk of harm (including physical, psychological, economic, or social harm).

This definition could include an unanticipated adverse device effect, any serious adverse effect on health or safety or any life-threatening problem or death caused by, or associated with, a device, if that effect, problem, or death was not previously identified in nature, severity, or degree of incidence in the investigational plan or application (including a supplementary plan or application), or any other unanticipated serious problem associated with a device that relates to the rights, safety, or welfare of subjects (21 CFR 812.3(s)).

7.3 **Classification of an Adverse Event**

7.3.1 **Severity of Event**

For AEs not included in the protocol defined grading system, the following guidelines will be used to describe severity.

- **Mild** – Events require minimal or no treatment and do not interfere with the participant's daily activities.
- **Moderate** – Events result in a low level of inconvenience or concern with the therapeutic measures. Moderate events may cause some interference with functioning.

CONFIDENTIAL

This material is the property of the NYU School of Medicine and Langone Medical Center. Do not disclose or use except as authorized in writing by the study sponsor

- **Severe** – Events interrupt a participant's usual daily activity and may require systemic drug therapy or other treatment. Severe events are usually potentially life-threatening or incapacitating.

7.3.2 Relationship to Study Agent

The clinician's assessment of an AE's relationship to study agent (drug, biologic, device) is part of the documentation process, but it is not a factor in determining what is or is not reported in the study. If there is any doubt as to whether a clinical observation is an AE, the event should be reported. All AEs must have their relationship to study agent assessed. In a clinical trial, the study product must always be suspect. To help assess, the following guidelines are used.

1. **Related** – The AE is known to occur with the study agent, there is a reasonable possibility that the study agent caused the AE, or there is a temporal relationship between the study agent and event. Reasonable possibility means that there is evidence to suggest a causal relationship between the study agent and the AE.
2. **Not Related** – There is not a reasonable possibility that the administration of the study agent caused the event, there is no temporal relationship between the study agent and event onset, or an alternate etiology has been established.

For all collected AEs, the clinician who examines and evaluates the participant will determine the AE's causality based on temporal relationship and his/her clinical judgment. The degree of certainty about causality will be graded using the categories below.

1. **Definitely Related** – There is clear evidence to suggest a causal relationship, and other possible contributing factors can be ruled out. The clinical event, including an abnormal laboratory test result, occurs in a plausible time relationship to drug administration and cannot be explained by concurrent disease or other drugs or chemicals. The response to withdrawal of the drug (dechallenge) should be clinically plausible. The event must be pharmacologically or phenomenologically definitive, with use of a satisfactory rechallenge procedure if necessary.
2. **Probably Related** – There is evidence to suggest a causal relationship, and the influence of other factors is unlikely. The clinical event, including an abnormal laboratory test result, occurs within a reasonable time after administration of the drug, is unlikely to be attributed to concurrent disease or other drugs or chemicals, and follows a clinically reasonable response on withdrawal (dechallenge). Rechallenge information is not required to fulfill this definition.
3. **Possibly Related** – There is some evidence to suggest a causal relationship (e.g., the event occurred within a reasonable time after administration of the trial medication). However, other factors may have contributed to the event (e.g., the participant's clinical condition, other concomitant events). Although an AE may rate only as "possibly related" soon after discovery, it can be flagged as requiring more information and later be upgraded to "probably related" or "definitely related," as appropriate.
4. **Unlikely to be related** – A clinical event, including an abnormal laboratory test result, whose temporal relationship to drug administration makes a causal relationship improbable (e.g., the event did not occur within a reasonable time after administration of the trial medication) and in which other drugs or chemicals or underlying disease provides plausible explanations (e.g., the participant's clinical condition, other concomitant treatments).
5. **Not Related** – The AE is completely independent of study drug administration, and/or evidence exists that the event is definitely related to another etiology. There must be an alternative, definitive etiology documented by the clinician.

CONFIDENTIAL

This material is the property of the NYU School of Medicine and Langone Medical Center. Do not disclose or use except as authorized in writing by the study sponsor

